2. LIST OF ABBREVIATIONS AND DEFINITION OF TERMS

Abbreviation	Definition
ADL	activities of daily living
AE	adverse event
Ae ₀₋₂₄	amount of FD001 excreted in urine from time 0 to 24 hours
AIDS	acquired immunodeficiency syndrome
AKI	acute kidney injury
BP	blood pressure
bpm	beats per minute
BUN	blood urea nitrogen
CI	confidence interval
CKD	chronic kidney disease
CKD-EPI	Chronic Kidney Disease Epidemiology Collaboration
CL _r	renal clearance
CL _{r0-24}	renal clearance from time 0 to 24 hours
CRU	clinical research unit
CYP	cytochrome P450
DILI	drug-induced liver injury
ECG	electrocardiogram
eCRF	electronic case report form
eGFR	estimated glomerular filtration rate
EOS	end-of-study
FD001	5 kD carboxymethyl dextran
FD003	150 kD carboxymethyl dextran
FDA	Food and Drug Administration
FSH	follicle-stimulating hormone
GCP	Good Clinical Practice
GFR	glomerular filtration rate
HBV	hepatitis B virus
HCV	hepatitis C virus
HIV	human immunodeficiency virus
HPLC	high performance liquid chromatography
HR	heart rate
ICH	International Council for Harmonisation
IEC	independent ethics committee
INR	international normalized ratio
IRB	institutional review board

Abbreviation	Definition
IV	intravenous(ly)
ISV	interstitial volume
IVV	intravascular volume
LOQ	limit of quantitation
MDRD	Modification of Diet in Renal Disease
mGFR	measured glomerular filtration rate
OTC	over-the-counter
PD	pharmacodynamic(s)
PK	pharmacokinetic(s)
PR (interval)	interval measured from the beginning of the P wave to the beginning of the QRS complex in the heart's electrical cycle as measured by electrocardiogram
PV	plasma volume
QRS (interval)	the interval between the Q wave and the S wave in the heart's electrical cycle as measured by electrocardiogram; principal deflection in the electrocardiogram
QT (interval)	a measure of the time between the start of the Q wave and the end of the T wave in the heart's electrical cycle as measured by electrocardiogram
QTc (interval)	QT interval corrected for heart rate
QTcF (interval)	QT interval corrected for heart rate using Fridericia's formula
RR (interval)	the time elapsed between 2 consecutive R waves as measured by electrocardiogram
SAE	serious adverse event
S _{cr}	serum creatinine
SRC	safety review committee
SRM	study reference manual
TEAE	treatment-emergent AEs
UADE	unanticipated adverse device effect
ULN	upper limit of normal
VFI	visible fluorescent injectate

4. INTRODUCTION AND BACKGROUND

4.1. Introduction

The mortality of patients on chronic hemodialysis (HD) remains high at 17% per year and similarly the 5-year survival rate is low at only 42% ([United States Renal Data System, 2018](#)), which is worse than for advanced colon cancer ([O'Connell et al, 2004](#)). Cardiovascular events are the leading cause of death ([United States Renal Data System, 2018](#)), and an important but often unrecognized cause for excess cardiovascular mortality on HD is volume overload. Volume overload contributes to hypertension ([Agarwal et al, 2009](#)) and left ventricular hypertrophy ([Hur et al, 2013](#)), both of which are associated with cardiovascular events and mortality ([Sarnak et al, 2003](#)). Experimental objective measures of volume status have directly associated volume overload with mortality ([Agarwal 2010](#); [Wizemann et al, 2009](#)).

Despite classical recognition for the importance of removing adequate volume with HD, volume overload remains common in the HD population. HD patients are hospitalized frequently, with an average of 1.7 hospitalizations per year with rehospitalization within 30 days of discharge occurring in 38% of discharges ([United States Renal Data System, 2018](#)), which is far in excess of the general population. Volume overload conservatively contributes to over 10% of both initial hospitalizations and readmissions within 30 days ([United States Renal Data System, 2018](#)), with 1 analysis finding a 14% yearly rate for acute dialysis performed for volume overload at a cost to Medicare of \$266 million in 2010 dollars ([Arneson et al, 2010](#)).

The persistent morbidity and mortality attributable to volume overload is in part due to the lack of a validated objective measure of volume status for the dialysis population ([Sinha 2011](#)). In the absence of an objective method, the subjective dry weight method is used to manage volume status on HD. The dry weight method remains essentially unchanged since it was first described over 60 years ago and it relies on the clinical interview and exam to detect volume overload ([Thompson et al, 1967](#)). Unfortunately, the clinical exam is not sensitive for detecting small but clinically relevant volume overload ([Sinha and Agarwal, 2009](#)), and changes in dry weight of only 0.6 to 1 kilogram have been shown to be clinically significant ([Agarwal et al 2009](#); [Hur et al, 2013](#)).

There is a clear and longstanding need for a reliable objective measure of volume status for use in guiding volume removal in the chronic HD population.

4.2. Investigational Device Background

The FAST PV and mGFR Technology is a direct measurement of PV and GFR that relies on reading the intensity of fluorescent markers attached to different sized dextran molecules introduced into the bloodstream. The test is intended as an adjunct to current methods utilized to assess kidney function, intravascular volume and interstitial volume.

The FAST PV and mGFR Technology includes intravenously (IV) administered fluorescent markers, timed blood draws, a validated fluorometric assay, and a computed algorithm to integrate the results and calculate the PV and GFR.

In cases where there near zero or zero kidney function, the FAST PV and mGFR Technology can be used to determine the interstitial volume of a patient. The distribution of the FD001, measured by timed blood samples, combined with the measured PV, allows for the ISV determination.

The FAST PV and mGFR Technology will aid in identifying and determining the extent of renal dysfunction, therefore promoting early treatment, including dialysis initiation, as well as enrollment and stratification for clinical studies. This technology could also be used to determine the effect of a clinical maneuver on GFR such as volume resuscitation.

4.3. Study Product Background

The bolus IV administered visible fluorescent injectate (VFI) agent is comprised of a mixture of 2 different molecular weight carboxymethyl dextran molecules (5 kD and 150 kD) with different fluorescent dye molecules attached. The 5 kD carboxymethyl dextran (FD001) is labeled with 5-aminofluorescein and the 150 kD carboxymethyl dextran (FD003) is labeled with 2-sulfohexamine rhodamine. These fluorescent labels are covalently attached to the dextran through the carboxymethyl moiety. When combined in a 3:1 (mass) ratio of small to large molecules, these dextrans make up the VFI.

The high molecular weight labeled carboxymethyl dextran, FD003, is not rapidly cleared from the vasculature and is not rapidly cleared by passive filtration in the kidneys; therefore, its concentration in the blood stream after injection provides a direct measurement of the total PV. The low molecular weight labeled carboxymethyl dextran, FD001, is also not subject to rapid metabolism but is freely filtered by the kidneys. The decline in the concentration of FD001 combined with the PV measured by FD003 provides a rapid and accurate assessment of GFR.

In previous studies, the FD001 component of the FAST VFI was used to determine mGFR. In this study, the FD001 marker will be used to measure the volume of distribution or interstitial volume (ISV). Its distribution into the interstitial space, combined with the measurement of PV by FD003 will allow for the calculation of a true measured volume of distribution.

While the VFI is a substantially modified dextran-based compound, other dextran products have, on rare occasions, been associated with mild to severe, acute anaphylactic reactions including death. As a precaution, subjects will be closely monitored for signs of allergy and anaphylaxis, and an emergency resuscitation kit and team will be available throughout the performance period.

4.4. Summary of Findings to Date

4.4.1. Nonclinical Studies

Nonclinical studies are summarized in Section 3 of the current FAST PV and mGFR Technology Investigator's Brochure.

4.4.2. *Effects in Humans*

4.4.2.1. **Summary of Clinical Findings**

FAST BioMedical has conducted 4 clinical studies evaluating the FAST PV and mGFR Technology in healthy subjects (Study FAST_GFR-01.1), in healthy subjects and subjects with compromised renal function (Study Pilot B/Phase 2a), in healthy subjects and patients with varying degrees of renal impairment (Study Phase 2b) and in hospitalized ADHF patients (Study Phase 2c).

The Phase 1 single-dose, dose-ranging clinical study was conducted in Germany with the FAST PV and mGFR Technology (Study FAST_GFR-01.1). In this study, 32 subjects divided into 4 cohorts of 8 subjects (6 subjects receiving the VFI and 2 subjects receiving placebo) between the ages of 21 and 45 years completed the study. Doses of the VFI evaluated in this study were 5, 15, 75, and 150 mg administered by slow bolus injection. The placebo subjects received 0.9% normal saline for injection. The components of the device used in the study included a catheter-based fiber optic probe placed in the subject's peripheral vein to allow the concentration of fluorescent markers to be monitored and an optical device to excite and detect the markers.

Single-dose administration of VFI in a range of 5 to 150 mg was safe and well tolerated. Overall, 9 subjects (28.1%) experienced 15 treatment-emergent adverse events (TEAEs), which were considered reasonably related to the VFI administration or study procedures by the investigator. Most related TEAEs were observed after administration of 15 mg VFI (9 TEAEs reported by 3 subjects). Two subjects (both receiving 15 mg VFI) reported 6 TEAEs (pruritus and gastrointestinal disorders), which were considered related to VFI (mainly injection site pain and hematoma at the blood sampling site). The most frequently reported TEAEs were nervous system disorders (10 subjects [31.3%], 10 TEAEs), which mainly included headache considered unrelated to the VFI or study procedures. All TEAEs were of mild to moderate intensity and there were no serious adverse events (SAEs); no subject discontinued the study due to an adverse event (AE). No treatment-related TEAEs were observed after the highest dose. There were no adverse device effects. Safety laboratory parameters, vital signs, and electrocardiogram (ECG) parameters showed no clinically relevant time- or treatment-related differences.

The Phase 2a clinical study was a prospective study evaluating the FAST PV and mGFR Technology in subjects with preserved and impaired kidney function. In this study, 4 cohorts of 8 subjects and 1 cohort of 6 subjects were planned to receive 75 mg of the VFI (50 mg FD001 and 25 mg FD003). A total of 33 subjects were enrolled with 1 of 6 planned subjects enrolled in the AKI group. Cohorts 1 and 5 had normal kidney function with GFR of ≥ 60 mL/min, Cohort 2 GFR was estimated at 30 to 59 mL/min, Cohort 3 GFR was 15 to 29 mL/min, and Cohort 4 was planned to be AKI subjects with $S_{cr} \geq 2$ -fold increase or eGFR > 50% decrease compared to baseline. Of the 33 subjects enrolled, 19 (57.6%) subjects experienced 37 TEAEs during the study. There were no treatment-emergent SAEs during the study. The majority of laboratory parameters were within normal ranges or considered not clinically significant. No clinically significant changes in vital signs were noted during the study. The majority of subjects had ECGs that were normal or had abnormalities that were considered not clinically significant. Two subjects, both with medical histories significant for cardiac disorders, had abnormalities that were considered to be clinically significant AEs.

The Phase 2b study was a prospective, open-label study designed to evaluate the safety, tolerability, pharmacokinetics (PK), and pharmacodynamics (PD) of FAST PV and mGFR Technology in healthy subjects and patients with varying degrees of renal impairment. A total of 32 subjects were planned to be enrolled in 4 cohorts of up to 8 subjects/patients each. Healthy subjects in Cohorts 1 and 2 had an eGFR ≥ 60 mL/min/1.73 m²; patients with impaired renal function in Cohort 3 had an eGFR ≥ 30 and < 60 mL/min/1.73 m²; and patients with impaired renal function in Cohort 4 had an eGFR ≥ 15 and < 30 mL/min/1.73 m². Subjects in Cohort 1 received a single dose of VFI followed 130 minutes later by a 350-mL infusion of 5% albumin in normal saline over 30 minutes on Day 1. Subjects in Cohort 2 received a dose of VFI followed 160 minutes later by a single dose of iohexol (refer to [Section 4.5](#) for additional information on iohexol) on Day 1 and a second dose of VFI 24 hours following the initial dose of VFI. Patients in Cohorts 3 and 4 received a single dose of VFI followed 160 minutes later by a single dose of iohexol on Day 1.

The FAST VFI was safe and well tolerated in healthy subjects in Cohorts 1 and 2 and in patients with impaired renal function in Cohorts 3 and 4. No severe or serious TEAEs, TEAEs leading to study drug discontinuation, or deaths were reported during the study. Overall, the majority of TEAEs reported were mild in severity. Three patients in Cohort 4 had a TEAE of blood creatine phosphokinase increased related to clinically significant abnormal creatine kinase levels. All 3 TEAEs of blood creatine phosphokinase increased were mild in severity and considered by the investigator to be possibly related to study drug. There were no other clinically significant abnormal clinical laboratory values. There were no clinically significant abnormal ECG or vital signs measurements, nor were there clinically meaningful trends identified in observed values or changes from baseline. There were no clinically significant abnormal physical examination findings.

The Phase 2c study was an investigator-initiated, human clinical trial designed to evaluate the safety and functionality of the FAST PV and mGFR Technology in hospitalized CHF patients. Patients enrolled in the study were administered VFI (Day 1) with a second dose occurring 48h (+/- 5h) after the initial dose (Day 3). A total of 37/50 (74%) patients had a treatment-emergent AE (TEAE) while 21/30 (42%) had a treatment-emergent SAE (TESAE). One patient died during the study, but the death was deemed to be not related to the intervention. Further, there were no treatment related SAEs and 10/50 (20%) patients had a treatment related AE with maximal mild severity. In total, 4 patients (4/50, 8%) suffered from treatment related diarrhoea including 1 with a moderate severity while for all other related TEAES only 1 patient was affected each time (1/50, 2%). Of all 50 patients, 3 patients (6%) were affected by pneumonia, cardiac failure, and acute kidney injury each while 2 patients had endocarditis. All other SAEs occurred only in 1 patient each (1/50, 2%).

4.4.2.2. Pharmacokinetics and Pharmacodynamics in Human Subjects

In the first-in-human clinical study (Study FAST_GFR-01.1), mean plasma concentrations of FD001 increased dose dependently with peak concentrations observed at 0.25 hours after administration (first blood sample). Thereafter, mean concentration decreased rapidly with no concentration above the limit of quantitation (LOQ) observed at 48 hours postdose. Mean plasma concentrations of FD003 increased dose dependently with peak concentrations observed at 0.25 (5 mg VFI) to 2 hours (75 and 150 mg VFI) after injection. Thereafter, mean concentrations decreased with a constant rate until 312 hours postdose. A slower elimination rate was observed until 480 hours after administration (end of the observation period). At 480 hours, all subjects in the 75- and 150-mg groups had concentrations of FD003 above the LOQ.

In the Phase 2a clinical study, following IV bolus injection of the VFI to patients with varying degrees of kidney function, FD001 generally reached maximum observed concentration following the end of the infusion and decreased in a multiexponential, first order elimination manner with early-phase distribution apparently complete at 8 to 12 hours. The mean time at which the maximum plasma concentration was observed was approximately 0.25 hours. Mean plasma elimination half-life estimates increased with decreasing renal function (5.64 hours in Cohort 5, 9.48 hours in Cohort 2, and 18.3 hours in Cohort 3). In contrast, mean plasma FD003 elimination half-life estimates were generally similar regardless of renal function (90.9 hours in Cohort 5, 123 hours in Cohort 2, and 125 hours in Cohort 3). Mean FD003 volume estimates indicated that FD003 appeared to occupy a volume space that corresponds to PV. Mean FD003 clearance did not change with decreasing renal function.

The Phase 2b clinical study showed that FD001 does not appear to accumulate in most healthy subjects with normal renal function when dosed at a 24-hour interval. The PK of the FAST VFI in patients with varying degrees of kidney function indicated the renal clearance of FD001 from 0 to 3 hours after dosing is indicative of GFR. The exposure to and elimination of FD003 was independent of renal function. FD003 distributed in a manner consistent with vascular volume. Additionally, FD003 remained stable in the vasculature for a period of at least 6 hours, allowing repeat measurements of PV during that time period without redosing.

The PV data showed good correlation and no bias when compared to Nadler's estimate (Nadler et al, 1962). A comparison of iohexol GFR to the FAST VFI mGFR showed excellent correlation through the entire range of GFRs measured. The FAST VFI method was able to accurately measure the change in PV within subjects due to the administration of 350 mL of 5% albumin. The FAST mGFR technology delivered clinically meaningful results as demonstrated by its ability to stratify patients by kidney function.

Pharmacokinetics were not studied in the Phase 2c study.

4.5. Iohexol Background

OMNIPAQUE 300 (hereafter referred to as iohexol) is indicated in adults for aortography including studies of the aortic arch, abdominal aorta and its branches, contrast enhancement for computed tomographic head and body imaging, cerebral arteriography, peripheral venography (phlebography), and excretory urography.

Following intravascular injection, iohexol is distributed in the extracellular fluid compartment and is excreted unchanged by glomerular filtration. It will opacify those vessels in the path of flow of the contrast medium permitting radiographic visualization of the internal structures until significant hemodilution occurs.

Approximately 90% or more of the injected dose is excreted within the first 24 hours, with the peak urine concentrations occurring in the first hour after administration. Plasma and urine iohexol levels indicate that the iohexol body clearance is due primarily to renal clearance (CL_r). An increase in the dose from 500 to 1500 mgI/kg does not significantly alter the clearance of the drug. The following PK values were observed following the IV administration of iohexol (between 500 to 1500 mgI/kg) to 16 adult human subjects: $CL_r = 120$ (86 to 162) mL/min; total body clearance = 131 (98 to 165) mL/min; and volume of distribution = 165 (108 to 219) mL/kg.

Renal accumulation is sufficiently rapid that the period of maximal opacification of the renal passages may begin as early as 1 minute after IV injection. Urograms become apparent in about 1 to 3 minutes with optimal contrast occurring between 5 to 15 minutes. In nephropathic conditions, particularly when excretory capacity has been altered, the rate of excretion may vary unpredictably, and opacification may be delayed after injection. Severe renal impairment may result in a lack of diagnostic opacification of the collecting system and, depending on the degree of renal impairment, prolonged plasma iohexol levels may be anticipated. In these patients, the route of excretion through the gallbladder and into the small intestine may increase.

Iohexol displays a low affinity for serum or plasma proteins and is poorly bound to serum albumin.

No significant metabolism, deiodination, or biotransformation occurs.

Iohexol enhances computed tomographic imaging through augmentation of radiographic efficiency. The degree of density enhancement is directly related to the iodine content in an administered dose; peak iodine blood levels occur immediately following rapid IV injection. Blood levels fall rapidly within 5 to 10 minutes and the vascular compartment half-life is approximately 20 minutes. This can be accounted for by the dilution in the vascular and extravascular fluid compartments which causes an initial sharp fall in plasma concentration. Equilibration with the extracellular compartments is reached in about 10 minutes; thereafter, the fall becomes exponential.

Refer to the [OMNIPAQUE \(iohexol\) injection prescribing information \(2010\)](#) for additional details.

4.6. Study Rationale

4.6.1. Rationale for Dose Selection

Each anticipated single dose for a 70-kg human will consist of 35 mg of FD001 and 12 mg of FD003, diluted at 15.7 mg/mL, for a total injection of 3.0 mL VFI, equivalent to 0.78 mg/kg or 28.9 mg/m² for a 60-kg human.

4.6.2. Rationale for Study Design

This is a pilot, single-center, open-label study designed to evaluate the safety, tolerability, and performance of the FAST PV Technology in chronic dialysis patients. The dosing schedule was determined based on anticipated clinical use.

Male and female subjects will be enrolled in the study. As no sufficient data are available on a potential influence of the VFI on embryo-fetal development, female subjects must be of non-childbearing potential or must provide confirmation of a known and medically acceptable contraception method. Reproductively active men must agree to either practice abstinence or utilize adequate contraception.

Subject safety will determine the progression or discontinuation of the study. In rare cases, dextran products have been documented to produce anaphylactic reactions in humans, and the onset of symptoms is documented to be acute. The VFI is a substituted dextran product that has shown little evidence of antigenicity in nonclinical studies.

The duration of confinement and medical surveillance are considered adequate to ensure safety of the subjects.

The FAST VFI has not been given to dialysis patients before. In the Phase 2c study, a patient with a measured GFR of 16.7 mL/min/1.73m² was dosed with VFI with no AE or SAEs related to the study drug observed. Although the patients in this study will receive 2 doses of FAST VFI, the initial doses of VFI and iohexol will be removed during the patient's dialysis session. The second dose of VFI and Iohexol will be removed between 36 and 48 hours later at the first follow-up dialysis session. The concentration the patients in this study will be exposed to is higher for longer than previous studies due to the lack of kidney function; however, the FD001 and iohexol, will continue to distribute into the extracellular fluid of the patient. The FD003 exposure is unchanged from prior studies.

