Study Design:	
This is a pilot, single-center, open-label study designed to evaluate the safety, tolerability, and performance of the FAST PV Technology in patients on chronic dialysis.
 
The planned dose cohorts are presented in the table below:
 
  
 Cohort	Population	eGFR^a	Base VFI Dose^b	Number of Doses	Comparator Dose	Number of Doses	Number of Subjects	
   
 1	Dialysis Patients	≤ 2 mL/min/1.73 m²	3 mL	2	Iohexol 5 mL	2	10	
  
 
Abbreviations: eGFR = estimated glomerular filtration rate; N/A = not applicable. ^a Patients must be on chronic hemodialysis for ≥ 3 months and oliguric defined as ≤ 2 urinary voids per day. ^b 3 mL for subjects/patients ≥ 40 and ≤ 100 kg + 1 mL for every 40 kg increase in body weight
 
Administration of VFI will occur within 28 days of screening.
 
Patients will receive 1 dose of VFI and 1 dose of iohexol approximately 4 hours prior to undergoing dialysis followed by a second dose of VFI and second dose of iohexol approximately 1 hour after completing dialysis. Patients will be discharged following completion of Day 1 activities. A follow-up visit will occur at the patient's next 2 dialysis appointments (approximately 2-3 days after Day 1) and 1 week after Day 1. A follow-up phone call will be performed on Day 31 (± 1 day).
							Cohort	Population	eGFR ^a	Base VFI Dose ^b	Number of Doses	Comparator Dose	Number of Doses	Number of Subjects	1	Dialysis Patients	≤ 2 mL/min/1.73 m ²	3 mL	2	Iohexol 5 mL	2	10
Cohort	Population	eGFR ^a	Base VFI Dose ^b	Number of Doses	Comparator Dose	Number of Doses	Number of Subjects																
1	Dialysis Patients	≤ 2 mL/min/1.73 m ²	3 mL	2	Iohexol 5 mL	2	10																
Subject Selection Criteria:	Males and females ≥ 18 will be enrolled in the study. Patients must be oliguric (have an estimated glomerular filtration rate (eGFR) ≤ 2 mL/min/1.73 m ²) and must be receiving maintenance chronic dialysis.																						
Investigational Product, Dose, and Route of	VFI, 3 mL for subjects/patients ≥ 40 and ≤ 100 kg + 1 mL for every 40 kg increase in body weight, bolus injection																						

Administration:	

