Abbreviations: BMI = body mass index; FD001 = 5 kD carboxymethyl dextran; FD003 = 150 kD carboxymethyl dextran; FSH = follicle-stimulating hormone; HBV = hepatitis B virus; HCV = hepatitis C virus; HIV = human immunodeficiency virus; VFI = visible fluorescent injectate.

^a. Assessments conducted upon enrollment will be used to reconfirm a subject's eligibility for enrollment into the study.

^b. Discharge procedures will be performed following completion of all Day 31 assessments. Subjects who terminate from the study early will have discharge procedures performed at the time of discontinuation.

^c. BMI will be calculated using the height obtained at screening.

^d. Medical and surgical history will be collected and documented to determine if any changes have occurred since screening.

^e. Vital signs will be measured after the subject has been resting quietly in a supine position or in the most recumbent position possible for at least 5 minutes.

^f. Vital signs will be measured within approximately 30 minutes prior to VFI and iohexol administrations and approximately 60-, 120- and 180-minutes post VFI and iohexol administrations.

^g. Refer to [Table 6](#) for a detailed list of clinical laboratory test parameters, which will be collected from the medical

Table 1. Schedule of Assessments and Procedures						
Study Procedure	Screening^a	Day 1		Follow-Up		Discharge^b
	Days -28 to -2	Dose 1	Dose 2	Day 3	Day 8	Day 31
record. h. BUN and serum creatinine will be drawn pre-dose dose 1 and post the dose 2 180 min VFI blood draw. i. Predose j. Pooled urine collection (from patient arrival to departure) to measure total volume, creatinine and urea nitrogen. No catheter. k. VFI administration of Dose 2 will occur approximately 8 hours following VFI administration of Dose 1 l. Blood samples to be drawn after dialysis session to allow for determination of any remaining FAST VFI. NOTE: In the event multiple postdose procedures are required to be conducted at the same nominal time point, the timing of performance blood sample collections will take priority over all other scheduled activities. In practice, the following order is recommended: (1) vital signs assessments; (2) performance blood sampling; (3) clinical laboratory tests sampling; (4) physical examination. Vital signs may be conducted up to 10 minutes prior to the nominal time to minimize the potential autonomic effects of blood draws on these measurements.						

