Table 2. Performance Sampling Schedule – (Two Performance Periods)					
Nominal Time Relative to Start of VFI Bolus Injection	FD001 and FD003 Plasma Sample	Iohexol Plasma Sample	Volume of Blood drawn^b	Timed Urine Collection	
Predose (within 30 minutes)	X	X	6 mL	Pool urine from patient arrival to departure.	
0 minutes	VFI and Iohexol Administration				
15 minutes	X	X	7 mL		
60 minutes	X	X	7 mL		
80 minutes	X		4 mL		
120 minutes	X	X	7 mL		
180 minutes	X	X	7 mL		
Dialysis Treatment (4 hours)					
Pre- Rinseback	X		4 mL		
Equilibrium time Post-Dialysis (1 hour)					
Predose (within 5 minutes of drug administration)	X	X	7 mL		
0 minutes	VFI and Iohexol Administration ^a				
15 minutes	X	X	7 mL		
60 minutes	X	X	7 mL		
80 minutes	X		4 mL		
120 minutes	X	X	7mL		
180 minutes	X	X	7 mL		

Blood Samples will be drawn at approximately the times listed in Table 2.2; however due to the nature of the study some variation in timing may occur. Regardless of the time and number of blood draws, no subject will have more than 80 mLs blood drawn for this study within a 24-hour period.
 
Abbreviations: FD001 = 5 kD carboxymethyl dextran; FD003 = 150 kD carboxymethyl dextran; VFI = visible fluorescent injectate.
 
^{a.} Second VFI and iohexol administration will occur approximately 8 hours after the initial administrations.
 
^{b.} Each blood draw will be taken as follows: 1 mL waste draw, 3mL FAST blood sample, 3 mL Iohexol Sample Note: Blood samples will be collected from the venous side of the arteriovenous fistula/graft. Performance blood samples will be collected as close to the nominal time point as possible. The allowable window for postdose blood sample collection relative to the start of VFI/iohexol bolus injection will be ±5 minute.
					

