6. STUDY DESIGN

6.1. Study Design and Overview

This is a pilot, single site, open-label study designed to evaluate the safety, tolerability, and performance of the FAST PV Technology in dialysis patients.

The planned dose cohorts are presented in [Table 3](#).

Cohort	Population	eGFR ^a	Base VFI Dose ^b	Number of Doses	Comparator Dose	Number of Doses	Number of Subjects
1	Dialysis Subjects	≤ 2 mL/min/1.73m ²	3 mL	2	Iohexol 5 mL	2	Up to 10

Abbreviation: N/A = not applicable

^a. Patients must be on chronic hemodialysis for ≥ 3 months and oliguric defined as ≤ 2 urinary voids per day.

^b. 3 mL for subjects/patients ≥ 40 and ≤ 100 kg + 1 mL for every 40 kg increase in body weight

Administration of VFI will occur within 28 days of screening.

Patients will receive 1 dose of VFI and 1 dose of iohexol approximately 4 hours prior to undergoing dialysis followed by a second dose of VFI and iohexol approximately 1 hour after completing dialysis. Patients will be discharged following completion of Day 1 activities. Patients will be seen and evaluated on their next 2 dialysis sessions for any adverse reaction by answering questions about their health, approximately on Day 3 and Day 8. A follow-up phone call will be performed on Day 31 (± 1 day).

Refer to [Table 1](#) for the Schedules of Assessments and Procedures.

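### Section 4.6.2 promises removal of the second dose within 36 to 48 hours, but nothing in the protocol prevents a three-day gap to the next dialysis, which makes it about 67 to 68 hours

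*Protocol*

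**What the plan says.** Section 4.6.2 argues that exposure is acceptable in patients who have almost no kidney function. It acknowledges that VFI has not been given to dialysis patients before and that they will be exposed to higher concentrations for longer than in earlier studies. It relies on dialysis to clear both doses, and for the second dose it says: "The second dose of VFI and Iohexol will be removed between 36 and 48 hours later at the first follow-up dialysis session".

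The timing of that follow-up session is described in three places:

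- **Synopsis, Study Design:** "A follow-up visit will occur at the patient's next 2 dialysis appointments (approximately 2-3 days after Day 1) and 1 week after Day 1".
- **Section 6.1:** patients are seen at their next two dialysis sessions, "approximately on Day 3 and Day 8". A tolerance of ± 1 day is printed for the Day 31 call, but none for Day 3.
- **Table 1:** a nominal Day 3 column carries CPK, liver tests and the residual-VFI sample. Footnote l requires the residual-VFI sample to be drawn after a dialysis session.

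The inclusion and exclusion criteria (7.1, 7.2) and the other restrictions (8.7.2) say nothing about the weekday of Day 1 or the interval to the next session.

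**The concern.** The 36 to 48 hour figure is stated as a fact about every patient, but it depends on a two-day gap that the protocol never requires. The synopsis names a range reaching three days. A patient dosed before the longer gap would carry the second dose of FD001 and iohexol well past the period on which the rationale relies.

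Two things are at stake.

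- **The safety argument.** Timely removal by dialysis is one of the few mitigations that section 4.6.2 offers for a first use in this population. Section 4.4.2.2 reports for FD001 that "Mean plasma elimination half-life estimates increased with decreasing renal function", and the patients here have an eGFR of at most 2 mL/min/1.73 m². In Phase 2b (section 4.4.2.1), "Three patients in Cohort 4 had a TEAE of blood creatine phosphokinase increased". That was the cohort with the lowest eGFR, and the events were judged possibly related.
- **Comparability of the follow-up samples.** In a patient with a three-day gap, the post-dialysis VFI sample and the CPK and liver samples tied to that visit would be taken about 24 hours later than in the others.

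**Working it through.** **Inputs**

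- Dose 1 is given about 4 h before dialysis (section 6.1).
- Dialysis lasts 4 h (Table 2).
- The interval before the second dose is "Equilibrium time Post-Dialysis (1 hour") in Table 2.
- Table 1 footnote k: "VFI administration of Dose 2 will occur approximately 8 hours following VFI administration of Dose 1". The separate parts add to 4 + 4 + 1 = 9 h, so both anchors are carried below.
- FD001 half-life is 18.3 h in Phase 2a Cohort 3, the most impaired cohort for which section 4.4.2.2 reports a value.

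**Step 1: when Dose 2 falls, relative to the start of Day 1 dialysis**

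- From Table 2: 4 + 1 = 5 h.
- From footnote k: 8 − 4 = 4 h.

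**Step 2: hours from Dose 2 to the start of the next session**

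Interval = 24 × (gap in days) − offset, assuming the next session starts at the same clock time as the Day 1 session. The protocol does not state that time.

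| Gap | Offset 5 h | Offset 4 h | Against 36-48 h |
|---|---|---|---|
| 2 days | 48 − 5 = 43 h | 48 − 4 = 44 h | inside |
| 3 days | 72 − 5 = 67 h | 72 − 4 = 68 h | 19-20 h over |

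The two-day row reproduces the protocol's statement. Adding the 4 h session, dialysis ends at 47-48 h with a two-day gap and at 71-72 h with a three-day gap.

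**Step 3: sensitivity to clock time**

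If the next session instead starts at the clock time of Dose 1, the interval is 24 × gap minus the time from Dose 1 to Dose 2 (9 or 8 h).

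- Two-day gap: 48 − 9 = 39 h or 48 − 8 = 40 h, still inside the stated range.
- Three-day gap: 72 − 9 = 63 h or 72 − 8 = 64 h, still at least 63 − 48 = 15 h over.

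**Step 4: FD001 exposure from Dose 2 to the next session, three-day against two-day gap**

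- No clearance between sessions (assumption): the ratio of times is 67/43 = 1.56 or 68/44 = 1.55.
- One compartment with half-life 18.3 h, k = ln 2 / 18.3 = 0.0379 per hour: (1 − e^(−67k)) / (1 − e^(−43k)) = 0.921/0.804 = 1.15. For 68 and 44 h the ratio is 1.14.

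Both ignore the distribution phase.

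**Step 5: share of patients affected**

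The protocol does not give this. If dialysis is three times a week (gaps of 2 + 2 + 3 = 7 days) and Day 1 is booked without regard to weekday, one session in three precedes the three-day gap. Both conditions are assumptions.

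**The case against.** The best reply is that the working schedule already implies a two-day gap. Table 1 has a Day 3 column, section 6.1 says about Day 3, and section 9 requires assessments at the Table 1 time points. Because the Day 3 sample must follow a dialysis session, a first follow-up session on Day 4 would miss the nominal visit. The synopsis parenthesis is also loosely drafted: it covers two appointments together, so it need not be a range for the first one.

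This shows what was intended, but it does not control booking. Day 3 is qualified as approximate, has no window and follows the patient's own dialysis schedule, while the synopsis mentions three days. The Day 3 sampling requirement itself needs a two-day gap, a condition that is nowhere written down.

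Other parts of the reply stand:

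- No harm is demonstrated. The protocol does not present 48 h as a safety threshold. The three CPK events were mild, those patients also received iohexol, and no link to duration of exposure is reported.
- CPK and liver tests are repeated on Day 8, and adverse events are collected to Day 31.
- The 55% figure is an upper bound that depends on zero clearance.
- Dose times and sample times are already recorded, so only the start of the next session is missing for deriving the interval.

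**Conclusion.** The concern holds. The 36 to 48 hour statement is correct for a two-day gap and wrong for the three-day gap that the protocol leaves open. In that case the next session starts about 67 to 68 hours after Dose 2, and the overrun is at least 15 hours under every clock-time variant tried.

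The extra FD001 exposure up to that session lies between about 14-15% and about 55%. With eGFR at or below 2, these patients should lie nearer the upper figure, but the protocol does not give their half-life. The proportion of patients affected is also unknown.

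The Day 1 plasma and interstitial volume endpoints are not touched, nor is the argument about FD003, which does not depend on renal function. The point is worth correcting before enrolment because the statement supports the safety case for a first use in dialysis patients and because the gap determines when the first follow-up safety samples are taken. It does not show that the study is unsafe.

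**What to change.** In section 6.1 and Table 1, require Day 1 to be booked on a session whose next scheduled dialysis is two days later, so that it starts within 36-48 hours of Dose 2. Change the 2-3 days in the synopsis to match. This makes section 4.6.2 true as written and aligns the Day 3 CPK, liver and residual-VFI samples across patients. It takes one booking line and one synopsis edit in an amendment; the price is fewer weekdays on which Day 1 can be scheduled.

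If that restriction is unworkable, restate the interval in section 4.6.2 as about 36-72 hours and justify that exposure. This keeps booking flexible but makes the exposure statement less favourable.

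In either case, record the hours from Dose 2 to the start of the next dialysis session for each patient.
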